8.5 Type and Duration of Follow-Up of Subjects after Adverse Events

SAEs will be followed until resolution even if this extends beyond the trial-reporting period. Resolution of an AE/SAE is defined as the return to pretreatment status or stabilization of the condition with the expectation that it will remain chronic.

8.6 Procedures to be Followed in the Event of Abnormal Laboratory Test Values or Abnormal Clinical Findings

Laboratory values will be graded according to [Appendix B](#). Abnormal laboratory values, performed as part of hematology, chemistry panel, or urinalysis but not listed in [Appendix B](#), will be evaluated by the study clinicians, recorded in the source document and, if clinically significant, considered AEs and graded according to the criteria details described in [Section 8.1](#).

The site principal investigator or appropriate sub-investigator is responsible for recording all AE and SAEs that are observed or reported during this study, regardless of the relationship to study product. AE and SAEs or abnormal clinical findings will be collected, assessed, documented, reported, and followed appropriately.

8.7 Halting Rules

8.7.1 Study Halting Rules

Trial dosing can be halted at any time if medically indicated. Trial dosing will be stopped, and all available safety data will be reviewed by the SMC if any of the following occur:

- Any SAE (regardless of the relationship to the study drug) throughout duration of study.
- 5 or more subjects in study (cumulative among all cohorts) experience a same grade 2 (or higher) related AE (laboratory or systemic) which is coded in the same high-level group term (HLGT) per MedDRA coding, throughout duration of study. Exception to this includes scenarios where there are obvious and acceptable physiological explanations for a Grade 2 or higher abnormality (e.g., Grade 3 hematuria in a menstruating female).
- Any subject experiences skin ulceration of any grade at an injection site.

8.7.2 Dose Escalation Halting Rules

Sentinel Subject Halting Rules

If any of the criterion below are met, the cohort will be suspended (enrollment and dosing), and the SMC ad hoc meeting will convene:

- Any SAE (regardless of the relationship to the study drug) through 48 hours post study drug administration.
- Any Grade 2 (or higher) adverse event deemed to be related to the study medication by the PI, having an initial onset within the first 72 hours post study drug administration that does not resolve within 72 hours from onset.
- Any subject experiences skin ulceration of any grade at an injection site.

Cohort Dose Escalation Halting Rules

If any of the criterion below are met, the escalation to the next cohort will be suspended (enrollment and dosing), and the SMC ad hoc meeting will convene.

- 2 or more subjects in a cohort experience the same grade 2 (or higher) related AE (laboratory or systemic) which is coded in the same HLTG per MedDRA coding, through Day 30 (SAD) or Day 30 (MAD) of the study.

- Two or more subjects within a cohort with post-dose QTcF > 500 or change from baseline >60 ms.
- Any subject experiences skin ulceration of any grade at an injection site.

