3.1.1 Dosing Scheme and Duration of Study

3.1.1.1 Part 1 (SAD)

In Part 1 of this trial, 44 subjects will be split into six cohorts – one cohort of 4 subjects (3 rezafungin, 1 placebo) and five cohorts of 8 subjects each (6 rezafungin, 2 placebo) – will be randomized to receive single SC doses of rezafungin or placebo with dose escalation separated by a minimum of 4 weeks. Single-dose levels of rezafungin to be assessed will follow an ascending single-dose regimen in all except Cohort 1. The 1, 10, 30, 60, and 100 mg doses will be administered as 0.1 – 1.0 mL SC injections (abdomen) and the 200 mg dose as 2 x 1 mL injections (in same abdominal quadrant). A schematic of the SAD study design is shown in (Table 1). Administration details are included in the protocol-specific Manual of Procedures (MOP) to this study.

Table 1: Design for SC Dosing in SAD (Study Part 1)

Cohort	Dose (mg)	Dose Volume (mL)	Number of Doses	Number of Subjects*	
				Rezafungin SC Injection	Placebo
1	1	0.1**	1	3	1
2	10	0.1	1	6	2
3	30	0.3	1	6	2
4	60	0.6	1	6	2
5	100	1	1	6	2
6	200	1 (in each of 2 injections) ***	1	6	2
Total Number of Subjects				33	11
					44

*Within each cohort two sentinel subjects will be admitted initially, and the randomization scheme will be designed to ensure that one subject will receive rezafungin and the other will receive placebo. All sentinel subject safety data through Day 30 will be reviewed by the PI prior to dosing the remainder of cohort. Safety data for each cohort through Day 30 will be confirmed by review of objective pre-defined criteria before continuing to the next cohort.

**In order to administer this dose, the drug product solution from the SC drug product vial (Rezafungin Injection, for subcutaneous use, 100 mg/mL) will be diluted 1:10 in 5% Dextrose Injection, USP. Then 0.1 mL of the diluted solution will be administered. Details are included in the MOP for this study.

***The 200 mg (2 x 1 mL) SC dose will be injected as 1 mL each in the same abdominal quadrant, separated by approximately 5 cm. Details are included in the MOP for this study.

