Cohorts 2-6 in the SAD and all MAD cohorts will be conducted with sentinel dosing of rezafungin (i.e., dosing in 2 subjects followed by remaining six subjects). The randomization scheme will be designed to ensure that 1 subject will receive rezafungin and the other will receive placebo in sentinel dosing. The dosing of the remaining six subjects in the same cohort will not be initiated until a minimum of 4 weeks after the second sentinel dosing, and no serious adverse events (SAEs)/adverse events (AEs) have occurred that meet the predefined objective halting criteria for sentinels. The blinded safety and clinical laboratory data from all subjects in the cohort will be reviewed and confirm that none of the dose-escalation halting rules have been met before moving to the next higher dose cohort. If any of the predefined halting criteria is met, the study enrollment and dosing will be stopped until the SMC provides recommendations regarding continuation of the study (See [Section 8.2.3](#)).

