10.3 Treatment Assignment Procedures

10.3.1 Randomization Procedures

Each subject who completes the Screening assessment, meets all eligibility criteria, and is enrolled into this trial will randomized to rezafungin or placebo (Cohorts 1-10) or randomized to treatment sequence (Cohort 11),, except for replacement subjects. Replacement subjects will be assigned the same study drug dosing regimen as the replaced subject.

The randomization schedule will be generated centrally through AdvantageEDCSM (Electronic Data Capture [EDC] System, Emmes) by the unblinded biostatistician, and a list will be transferred to the unblinded Site Pharmacist before the start of this trial as an emergency back-up. Part 1 Cohort 1 will have 4 subjects randomized 3:1 to receive rezafungin or placebo, respectively. There will be no sentinel dosing for Cohort 1. Within cohorts 2-6 in Part 1 and all cohorts of Part 2, 8 subjects will be randomized 3:1 to receive rezafungin or placebo, respectively. In each dosing cohorts 2-6 in Part 1 and all cohorts of Part 2, the first two subjects will be randomized 1:1 to receive rezafungin or placebo to ensure that one of the first two subjects receives rezafungin and the other placebo. The study drug assignment of the remaining subjects in each cohort will be randomly assigned in a 5:1 ratio of active drug to placebo to ensure the 3:1 ratio for the entire dosing cohort. In Part 3, 10 subjects will be randomized in a 1:1 ratio of dose route order (SC → IV or IV → SC). Enrollment will occur at one CRU.

Per ICH guideline E6: GCP, screening records that document why an individual was screened but not enrolled will be kept at the CRU. Reasons for screen failures will also be recorded in AdvantageEDCSM.

Subjects will be enrolled online using the enrollment module of AdvantageEDCSM. The randomization code will be prepared by statisticians at the SDCC and included in the enrollment module for this trial. AdvantageEDCSM will assign each subject to a rezafungin or placebo group after demographic and eligibility data have been entered into the system. A designated individual at the CRU will be provided with a code list for emergency unblinding purposes, which will be kept in a secure place.

Instructions for using the enrollment module are included in the AdvantageEDCSM User's Guide. Manual back-up procedures and instructions are provided for use in case the CRU temporarily loses access to the Internet or the online enrollment system is unavailable.

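### Protocol 8.7.2 has no automatic SMC trigger for one non-serious related Grade 3 event or marked QTcF prolongation in the only active sentinel when it starts after 72 h, or starts earlier and clears within 72 h

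*Protocol*

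**What the plan says.** Sentinel dosing applies to Cohorts 2 to 6 of Part 1 and to all four cohorts of Part 2 (Protocol 3.1.3 and 10.3.1). Of the first two subjects, one gets rezafungin and one placebo. The treatment of the other six "will be randomly assigned in a 5:1 ratio of active drug to placebo". Dosing of those six "will not be initiated until a minimum of 4 weeks after the second sentinel dosing", and requires that no SAEs or AEs "have occurred that meet the predefined objective halting criteria for sentinels".

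The sentinel rules in 8.7.2 have three criteria:
- an SAE within 48 h of dosing;
- a Grade 2 or higher AE that the PI judges related, "having an initial onset within the first 72 hours post study drug administration that does not resolve within 72 hours from onset";
- an injection-site ulcer of any grade.

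Meeting any one suspends the cohort and convenes the SMC.

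The other rules use higher counts. The cohort AE rule needs at least two subjects with the same related Grade 2 or higher event through Day 30. The cohort ECG rule reads "Two or more subjects within a cohort with post-dose QTcF > 500 or change from baseline >60 ms". The study rules in 8.7.1 need five subjects with the same related Grade 2 or higher event, or any ulcer, or the following: "Any SAE (regardless of the relationship to the study drug) throughout duration of study".

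The footnotes to Tables 1 and 2 add a review step: "All sentinel subject safety data through Day 30 will be reviewed by the PI prior to dosing the remainder of cohort".

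**The concern.** The hold exists so that one exposed subject is observed before five more are exposed. It lasts at least 4 weeks, but the AE criterion that governs release looks only at onsets in the first 72 h, and then only at events that persist. The cohort AE rule counts events through Day 30, so the protocol already treats late events as relevant to escalation. It gives them no automatic weight at the step where a single active subject is meant to protect five others.

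The ordering is also hard to defend. A related Grade 2 event at 24 h lasting 96 h goes to the SMC, while a related Grade 3 event at 73 h need not.

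Late findings are possible. This is the first subcutaneous use in humans (2.3.1). The half-life supports weekly or longer dosing (2.2.1), and plasma is sampled to Day 30. At stake is whether the SMC sees such a finding before the remaining six subjects are dosed, or only if someone chooses to refer it.

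**Working it through.** **1. Allocation.** Sentinels 1 active and 1 placebo, remainder 5 and 1: (1+5):(1+1) = 6:2 = 3:1, as planned. Totals: 4 + 5×8 = 44 in Part 1, 4×8 = 32 in Part 2, and 44 + 32 + 10 = 86, matching Protocol 10.2. Sentinel cohorts number 5 + 4 = 9. Cohort 1 has none.

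**2. Rules applied to one related, non-serious, non-ulcer event in the active sentinel.**

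| Event | Rule met |
|---|---|
| Grade 2 or 3, onset 24 h, lasts 96 h | Sentinel AE rule |
| Grade 3, onset 24 h, lasts 48 h | None |
| Grade 3, onset 73 h, 144 h or 300 h | None |

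The cohort rules need two subjects, when only one active and one placebo subject have been dosed. The study rule needs five. The exceptions are narrow: the event is the fifth in its MedDRA high-level group term, or the placebo sentinel has the same finding. There is no sentinel QTcF rule, so a QTcF finding judged unrelated meets no sentinel criterion at any time.

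**3. Scheduled assessments relative to 72 h (Appendix A, Tables 11 and 12).**
- Part 1 laboratory draws on Day 2 (24 h), Day 7 (144 h) and Day 30: 2 of 3 fall after the window.
- Part 1 post-dose ECGs at 4 h, Day 7 and Day 30: 2 of 3 fall after it.
- Part 2 through Day 30, if the window restarts at each dose: laboratory draws on Days 7, 14 and 21 fall outside (3 of 6), as do ECGs on Days 21 and 30 (2 of 5).
- Part 2, if the window runs from the first dose only: 5 of 6 draws and 4 of 5 ECGs fall outside.

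The window covers 72/696 = 10.3% of the hours to Day 30. That describes the window, not the share of events missed.

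The schedule alone also cannot always settle the persistence test. In Part 1 the next draw after 24 h is 120 h later, and the next ECG after 4 h is 140 h later.

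**4. Size.** The documents give no event rate. Let q be the assumed chance, per sentinel, of a qualifying event that meets no current rule.
- Active subjects then dosed without an automatic trigger, if nobody stops by discretion: 9 × q × 5 = 45q.
- Extra SMC meetings under the fix, counting both blinded sentinels: 9 × (1 − (1−q)²).

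| q | 45q | Extra meetings |
|---|---|---|
| 0.5% | 0.23 | 0.09 |
| 1% | 0.45 | 0.18 |
| 2% | 0.90 | 0.36 |
| 5% | 2.25 | 0.88 |

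**The case against.** The strongest reply is that release is not passive. The PI must review all sentinel data through Day 30. The PI or the Medical Monitor may stop dosing, and SMC review must then follow (8.2.3). Dosing can be halted whenever medically indicated (8.7.1), and DMID or the SMC may call an ad hoc meeting (8.8.2). The PI or Sponsor may class an important medical event as serious (8.1.2), which stops the trial. All ECGs are read by the PI or a designee (7.1.6), and neuropathy, tremor and phototoxicity go promptly to the Sponsor (8.1.3). All of this stands. A reader might infer that late sentinel events go unwatched; the documents do not support that. But each of these steps is discretionary or concerns review or reporting only. The Day 30 review has no stated threshold, the PI is blinded, and no SMC meeting is scheduled between the sentinels and the rest of a cohort.

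The risk evidence is also limited, and this too stands. Decreased potassium was reported in IV-treated patients with candidemia or invasive candidiasis, not in healthy adults. Abnormal liver tests are a class effect. Section 2.3.1 describes most events after IV dosing as mild and all as transient. The one cardiac conduction event it mentions was serious, so 8.7.1 would already catch it. No onset times are given. A reader might cite the monkey lesion seen on Day 12 at a Day 3 site (9 days, 216 h), but that followed dosing every 3 days. A single 30 mg/kg dose was well tolerated, and ulcers already have a rule without a time limit.

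Finally, the figures depend on assumed rates, and 45q counts doses given without SMC review, not harms.

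**Conclusion.** The gap is confirmed from the text, in a limited form. For one non-serious, non-ulcer related Grade 3 event or marked QTcF prolongation in the active sentinel, starting after 72 h or clearing within 72 h, SMC review before five more active subjects are dosed generally depends on someone's judgement. At assumed rates of 0.5% to 5%, at most 0.23 to 2.25 active subjects over nine cohorts are affected. That is an upper bound because it supposes no discretionary stop.

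Three stronger inferences fail:
- Late SAEs are not missed. Section 8.7.1 covers any SAE throughout, despite the 48 h limit in the sentinel rule.
- The Part 2 counts of 5 of 6 draws and 4 of 5 ECGs need the window to run from the first dose only. With dosing on Days 1, 8 and 15, restarting is the more natural reading, though the text does not state it.
- The termination for safety concerns does not show that this gap mattered. The SAP preface does not say what the concerns were.

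Only Cohorts 1 and 2 enrolled, and Cohort 1 had no sentinels. No SAP analysis changes. The point bears on the plan as written or a successor subcutaneous protocol, where the change is worth making because it costs little.

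**What to change.** In 8.7.2, keep the existing Grade 2 or higher persistence rule and add one sentinel criterion:

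*Any related Grade 3 AE (laboratory or systemic; starred local reactions in Appendix B excluded), or any post-dose QTcF >500 ms or change from baseline >60 ms regardless of relatedness, with onset at any time from first dose through the Day 30 sentinel review, whether or not it has resolved.*

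Meeting it suspends the cohort and convenes the SMC. Covering every onset time avoids a new step at 72 h, where a severe event at 60 h would be treated more leniently than one at 73 h. Dropping the resolution condition lets the rule act on a finding first seen at the Day 30 visit. The QTcF limits are those the protocol already uses at cohort level. Late Grade 2 events stay with the PI's review, and unstarred local reactions such as nodules stay under the existing rule.

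State that in Part 2 the 72 h window of the existing rule restarts after each dose. As housekeeping only, align the 48 h sentinel SAE window with 8.7.1.

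The cost is protocol wording. The laboratory, ECG and AE data, and the hold, are already planned. The downside is an occasional extra ad hoc SMC meeting, fewer than one expected over the nine cohorts at assumed rates up to 5% per sentinel, and possibly a longer hold for that cohort.

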3.1.3 Dose Escalations

In Part 1/SAD, the initial cohort of 4 subjects will be administered 1 mg of rezafungin (3 subjects) or placebo (1 subject) as a single SC injection.

Dose escalation to each successive cohort during Part 1 will occur if none of the predefined dose escalation halting criteria are met through Day 30 (final visit). The FDA will review all safety and PK data from the SAD (Part 1) and determine if the study may proceed to the MAD (Part 2) and BA (Part 3) portions. Rezafungin doses for the MAD and BA portions will be determined after FDA review of the SAD data. Dose escalation during Part 2 will occur if none of the predefined dose escalation halting criteria are met through Day 30 after the first dose. This will be communicated through the following process:

1. An email from the site to the SDCC attesting that all data entry has been completed after the last subject has had their Day 30 visit, then data cleaning, as applicable, prior to the SDCC being able to generate the report.
2. A halting criteria report will be provided by the SDCC to DMID.
3. If based on the entered data in EDC, none of the escalation criterion is met, then the SDCC will open the database for the following cohort after confirmation from DMID that the study may proceed to the next cohort.
4. If any of the criterion is met, the SDCC will provide the dose escalation report and an ad-hoc SMC meeting will be convened to seek recommendation from the SMC.

Part 2 (MAD) and Part 3 (BA) may not begin until after FDA has reviewed all safety and PK data from Part 1 (SAD) and given agreement that it is safe to proceed. The doses for Parts 2 and 3 may be updated after FDA review of the SAD data. There will be a scheduled SMC data review meeting prior to start of Part 2 (MAD) Cohort 7.

In order to efficiently identify the optimal therapeutic doses for use in future clinical trials, a flexible scheme of dose escalation, (based on ongoing study data) will be used that allows intermediate doses higher or lower than the planned doses (30, 60, 100, and 200 mg), upon protocol amendment and with IRB approval. However, no cohort will be dosed higher than the 200 mg free base equivalent.

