8.2.3 Dose Escalation Criteria

Dose escalation to each successive cohort of subjects will occur if none of the predefined dose escalation halting criterion is met (for all subjects through Day 30 [SAD] or Day 30 [MAD]). The SDCC will provide notification to the PI upon analysis of data for the cohort (for all subjects through Day 30 [SAD] or Day 30 [MAD]) for halting criteria as described in [Section 8.7 Study](#)

Design, Objectives and Endpoints or Outcome Measures, Dose Escalation. If any of the criterion for dose escalation is met, or, at the discretion of the PI or DMID Medical Monitor, the study enrollment and dosing will be stopped until the SMC reviews the data and provides its recommendations. There will be a scheduled SMC data review meeting prior to start of Part 2 (MAD).

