10.4 Planned Interim Analyses

10.4.1 Interim Safety Review

An interim safety review will be performed upon completion of the SAD cohorts (1-6) and prior to starting the MAD and BA parts of the study.

An interim safety review will also be performed by the SMC upon completion of Day 30 for all subjects upon completion of the SAD cohorts (1-6) and prior to starting the MAD and BA parts of the study. This safety review may include but is not limited to enrollment, laboratory, and safety data. If criteria for halting the trial (as listed in [Section 8.7](#)) are met, an *ad hoc* SMC meeting will be held to review all available safety data and to make recommendations about the dosing of all further subjects in the trial. The SMC will receive data presented in aggregate (by cohort). Analysis by treatment assignment may be provided to the SMC in the closed session only.

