Appendix B. TOXICITY TABLE

Clinical Adverse Events			
VITAL SIGNS	Mild (Grade 1)	Moderate (Grade 2)	Severe Grade 3
Fever - °C	38.0-38.4	38.5-38.9	>38.9
Tachycardia - bpm	101-115	116-130	>130 or ventricular dysrhythmias
Bradycardia – bpm • Baseline ≥60 OR, if Baseline <60	• 50-54 OR, if Baseline <60, • 45-50	• 45-49 OR, if baseline <60, • 40-44	• <45 OR, if baseline <60 • <40
Hypertension (systolic) - mmHg	141-150	151-160	>160
Hypertension (diastolic) - mmHg	91-95	96-100	>100
Hypotension (systolic) - mmHg	85-89	80-84	<80
Tachypnea – breaths per min	23-25	26-30	>30
CARDIOVASCULAR	Mild (Grade 1)	Moderate (Grade 2)	Severe Grade 3)
Arrhythmia		Asymptomatic; transient signs; no medical intervention required	Recurrent/persistent; symptomatic medical intervention required
Hemorrhage, Blood Loss	Estimated blood loss ≤100 mL	Estimated blood loss >100 mL; no transfusion required	Transfusion required

QTc (Fridericia's correction) ¹	Asymptomatic, QTc interval 450-479 msec	Asymptomatic; QTc interval 480 to 499 msec OR Increase in interval 30-59 msec above baseline	Asymptomatic; QTc interval \geq 500 msec OR Increase in interval \geq 60 msec above baseline
PR Interval (prolonged) ¹	PR interval 0.21-0.25 sec	PR interval >0.25	Type II 2 nd degree AV block OR Ventricular pause >3.0 sec
RESPIRATORY	Mild (Grade 1)	Moderate (Grade 2)	Severe (Grade 3)
Cough	Transient; no treatment	Persistent cough	Interferes with daily activities
Bronchospasm, Acute	Transient; no treatment; FEV1 71-80% of predicted peak flow	Requires medical intervention; normalizes with bronchodilator; FEV1 60-70% of predicted peak flow	No normalization with bronchodilator; FEV1 $<60\%$ of predicted peak flow
Dyspnea	Does not interfere with usual and social activities	Interferes with usual and social activities; no treatment	Prevents daily and usual social activity OR requires treatment
GASTROINTESTINAL	Mild (Grade 1)	Moderate (Grade 2)	Severe (Grade 3)
Nausea	No interference with activity	Some interference with activity	Prevents daily activities
Vomiting	No interference with activity OR 1-2 episodes/24 hours	Some interference with activity OR >2 episodes/24 hours	Prevents daily activity OR requires IV hydration OR requires medical intervention

¹Inclusion dependent upon protocol requirements.

Diarrhea	2-3 loose or watery stools or <400 g/24 hours	4-5 loose or watery stools or 400-800 g/24 hours	≥6 loose or watery stools or >800g/24 hours OR requires IV hydration OR requires medical intervention

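### Section 8.7.2 states a narrower stop for two cohort rules than 3.1.3 and 8.2.3 do, and no scheduled check of those rules falls before Part 2 doses 2 and 3

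*Protocol*

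**What the plan says.** Protocol 8.7.2 has two sets of rules with different consequences. If a sentinel rule is met, "the cohort will be suspended (enrollment and dosing" (the bracket closes in the original). If a cohort rule is met, "the escalation to the next cohort will be suspended (enrollment and dosing), and the SMC ad hoc meeting will convene". Three cohort rules follow:

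- two or more subjects with the same related Grade 2 or higher AE, matched by MedDRA high-level group term, through Day 30;
- two or more subjects with post-dose QTcF above 500 or a change from baseline above 60 ms;
- any injection-site ulcer.

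Two other sections state what follows when such a criterion is met. Section 3.1.3: "If any of the predefined halting criteria is met, the study enrollment and dosing will be stopped until the SMC provides recommendations". Section 8.2.3 has one sentence with two alternative triggers. The first is mandatory, namely that any dose-escalation criterion is met. The second is discretionary. Both lead to the same stop: "at the discretion of the PI or DMID Medical Monitor, the study enrollment and dosing will be stopped until the SMC reviews the data".

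On timing, step 1 of the process in 3.1.3 is an email from the site "attesting that all data entry has been completed after the last subject has had their Day 30 visit". The SDCC report follows and, if a criterion is met, "an ad-hoc SMC meeting will be convened to seek recommendation from the SMC". Section 8.2.3 likewise ties the SDCC's notification of the PI to cohort data through Day 30.

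**The concern.** Staff who need to know what a triggered rule requires will go to the halting-rule section. For the AE and QTcF rules it tells them to hold the next cohort and does not mention doses still due in the cohort that triggered. The paragraph just above it suspends the cohort itself, so the change of wording can be taken as a deliberately lighter consequence.

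In Part 1 this hardly matters, because each subject receives one dose. In Part 2 each subject receives three weekly doses, and either rule can be met after the first. Stopping an affected individual under 8.7.3 does not settle whether the rest of the cohort is dosed. What is at stake is whether the protocol's own stop takes effect in time to cover doses 2 and 3.

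**Working it through.** **1. Which rules are affected.** The ulcer rule is not, because 8.7.1 already stops all trial dosing for any ulcer. The AE and QTcF rules remain.

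**2. Scope, side by side.**

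| Section | Trigger | What stops |
|---|---|---|
| 8.7.2, sentinel | sentinel rule met | the cohort |
| 8.7.2, cohort | two-subject AE or QTcF rule met | escalation to the next cohort; current doses not mentioned |
| 3.1.3 | any predefined halting criterion met | study enrollment and dosing |
| 8.2.3 | any dose-escalation criterion met, or PI or Medical Monitor discretion | study enrollment and dosing |

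The last two rows are mandatory at two subjects. The second row is narrower but does not conflict with them.

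**3. Can a rule be met before dose 2 or dose 3?** Post-dose data scheduled in 6.5.1 to 6.5.7:

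- before dose 2 (Day 8): ECG 4 h after the Day 1 dose (one timepoint) and laboratory draws on Days 2 and 7 (two);
- before dose 3 (Day 15): ECG after the Day 1 and Day 8 doses (two timepoints) and draws on Days 2, 7, 9 and 14 (four).

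AEs are assessed daily while subjects are inpatients. So yes, either rule can be met in time to matter.

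**4. When must anyone check?** The scheduled check follows the last subject's Day 30 visit. Dose 3 is on Day 15, and 30 − 15 = 15 days. The check comes at least about two weeks after the final dose. Section 6.5.1 requires an eligibility re-check on Days 8 and 15, but it is per subject and leaves out exclusions 6 (laboratory values) and 7 (ECG). It counts nothing across the cohort.

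**5. Other halts.** The AE rule in 8.7.1 needs five subjects. That section has no QTcF bullet, although Appendix B grades QTcF (Grade 2 is "QTc interval 480 to 499 msec OR Increase in interval 30-59 msec above baseline"), so related QTcF events could arguably count toward the five. Section 8.7.3 lists SAEs, ulcers and PI judgement for the individual.

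**6. Size.** Under 10.3.1 the six non-sentinel subjects in a Part 2 cohort are randomized 5:1, giving 5 rezafungin and 1 placebo. If they are dosed together:

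- rule met by Day 7, nobody held: 6 × 2 = 12 administrations, of which 5 × 2 = 10 rezafungin;
- same, but two affected rezafungin subjects held by the PI: (6 − 2) × 2 = 8, of which (5 − 2) × 2 = 6 rezafungin;
- rule first met between dose 2 and Day 14, nobody held: 6 × 1 = 6, of which 5 × 1 = 5 rezafungin.

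**7. Likelihood.** The documents give no event rate. For an assumed per-subject rate p of the same qualifying event after dose 1, independent across the 5 rezafungin subjects, P(X ≥ 2) = 1 − (1 − p)^5 − 5p(1 − p)^4:

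| p | (1 − p)^5 | 5p(1 − p)^4 | P(X ≥ 2) |
|---|---|---|---|
| 0.05 | 0.7738 | 0.2036 | 0.023 |
| 0.10 | 0.5905 | 0.3281 | 0.081 |
| 0.20 | 0.3277 | 0.4096 | 0.263 |
| 0.30 | 0.1681 | 0.3602 | 0.472 |

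The rule counts all subjects in the cohort. These figures leave out the rezafungin sentinel and the placebo subjects, any of whom could supply an event.

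**The case against.** The strongest reply is that the question is already answered. Sections 3.1.3 and 8.2.3 impose an explicit, mandatory stop at two subjects, and they cross-refer to 8.2.3 and 8.7 respectively. Silence in 8.7.2 does not undo that, and its bracketed mention of enrollment and dosing can itself be read broadly. Nor must the SMC wait for Day 30. Section 8.7.2 convenes it when a rule is met, 10.4.1 says an ad hoc meeting will be held "to make recommendations about the dosing of all further subjects in the trial" if the 8.7 criteria are met, and 8.8.2 lets DMID or the SMC call one over any concern. The Day 30 process is the gate for opening the next cohort. The PI also sees these inpatients daily and may stop dosing on judgement.

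Most of this stands. It disposes of three stronger readings that a reader might infer:

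- That the protocol allows doses 2 and 3 after a trigger, or contradicts itself. It does neither, since 8.7.2 never says current dosing continues.
- That no mandatory rule covers two to four affected subjects. Sections 3.1.3 and 8.2.3 do.
- That no SMC meeting can be held before Day 30. The text does not say so.

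What the reply does not supply is a required step, before dose 2 or dose 3, at which someone establishes that a rule has been met. A mandatory stop depends on the trigger being recognised. One trigger needs a count across subjects by coded term, and the only scheduled count comes after dosing has finished. Alertness and discretion may fill that gap, but the protocol does not require it.

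**Conclusion.** The point holds as a mismatch of scope together with a missing within-cohort check. It should be fixed in the protocol text. The ceiling is 10 rezafungin doses (12 administrations) per Part 2 cohort. It assumes that all six non-sentinel subjects are dosed together, the rule is met by Day 7, nobody acts on the trigger or on 3.1.3 and 8.2.3 before Day 30, and nobody is held by discretion. The calculated likelihoods, from about 2% to 47%, rest entirely on assumed rates and independence. They show only that two events within a week are not far-fetched, not that a site would miss them.

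Nobody was exposed through this gap, and no analysis is affected. The SAP preface records that the study was terminated with no multiple-dose cohort enrolled. The point matters for any reuse of this multiple-dose design.

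**What to change.** Amend the cohort rules in 8.7.2 to read: *If a cohort rule is met at any time, study enrollment and dosing, including remaining doses in the affected cohort and any cohort running in parallel, are stopped until the SMC has reviewed the data (see 8.2.3).* The parallel cohort must be named because 3.1.1.3 allows Part 3 to run alongside Cohort 7. A sentence covering only the affected cohort would still be narrower than 3.1.3 and 8.2.3.

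Add to 6.5.1: *Before the Day 8 and Day 15 doses, the PI checks the AE, laboratory and ECG data then available against the AE and QTcF cohort rules, using clinical judgement of whether events are the same pending HLGT coding.* The Day 30 SDCC report stays as the gate to the next cohort.

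The cost is two sentences and no new assessments. The PI makes a short pre-dose check in every Part 2 cohort, not only in those that trigger. In a cohort that triggers, a weekly dose and its PK schedule may be delayed. The laboratory check is tight, since Day 7 samples (144 h) precede the Day 8 dose (168 h) by about 24 h. The QTcF check rests on only one post-dose ECG timepoint before dose 2 and two before dose 3.
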